8.9 Pharmacokinetic Analysis

Concentrations of APR-246 will be determined using validated bioanalytical methods.

During the APR-246 monotherapy cycle, PK sampling for APR-246 will be performed on Day 1 and 2. Noncompartmental PK analysis will be used to determine C_{max} , T_{max} , AUC and bioavailability after oral dosing for decision making on dose escalation of the oral dose.

PK sampling for APR-246 will be performed during Cycle 2, on Day 1, 8 and 15 and on Day 1 from Cycle 3 onwards.

PK sampling for venetoclax and rituximab will not be performed for this study.

The PK of APR-246 will be summarized using descriptive statistics (mean, standard deviation, CV% mean, geometric mean, CV% geometric mean). The concentration data for APR-246 will be evaluated using (popPK analysis in combination with data from other studies.

APR-246 AUC and C_{max} will then be tested for association with signs of efficacy and safety. If an observable trend exists, a PK/PD model will be developed to evaluate the exposure-response relationship between APR-246 plasma exposure and outcome measures. Demographic and clinical

data (ethnicity, current age, body weight, sex, disease status, etc.) will be utilized to assess interpatient variability in the PK and PK/PD relationships.

9.0 QUALITY CONTROL AND QUALITY ASSURANCE PROCEDURES

9.1 Monitoring of the Study and Regulatory Compliance

The project manager, or designee, will make an initiation site visit to each institution to review the protocol and its requirements with the Investigator(s), inspect the drug storage area, fully inform the Investigator of his/her responsibilities and the procedures for assuring adequate and correct documentation. During the initiation site visit the eCRFs will be reviewed. Other pertinent study materials will also be reviewed with the Investigator's research staff. During the course of the study, the monitor will make regular site visits in order to review protocol compliance, examine eCRFs and individual patient's medical records and assure that the study is being conducted according to pertinent regulatory requirements. All eCRF entries will be verified with source documentation. The review of medical records will be done in a manner to assure that patient's confidentiality is maintained.

9.2 Curricula Vitae and Financial Disclosure of Investigators

All Principal Investigators will be required to provide a current signed and dated curriculum vitae, a completed FDA Form 1572 and a financial disclosure statement to Sponsor's monitoring CRO. All Sub-Investigators will be required to provide a current curriculum vitae and a financial disclosure statement to Sponsor's monitoring CRO.

9.3 Protocol Modifications

No modification of the protocol should be implemented without the prior written approval of the Sponsor or the Sponsor's representative. Any such changes which may affect a patient's treatment or informed consent, especially those increasing potential risks, must receive prior approval by the IRB/IEC. The exception to this is where modifications are necessary to eliminate an immediate hazard to trial patients, or when the change involves only logistical or administrative aspects of the trial (e.g., change in monitor, change in telephone number). Other administrative revisions which may impact the clinical portion of a study will be duly reported to the IRB/IEC by the Principal Investigator.

9.4 Publication Policy

The publication of the results of the study will be subject to the terms and conditions of the clinical trial agreement between the Sponsor and Investigators. Sponsor approval is required for publication of any data from this trial.

10.0 ETHICAL CONSIDERATIONS

10.1 Informed Consent

The Investigator will obtain written informed consent from each patient, or their authorized representative, participating in the study. The form must be signed, witnessed and dated. The

informed consent form will contain all the Essential Elements of Informed Consent set forth in 21 CFR, Part 50, the European Union Directive 2001/20/EC and its associated Detailed Guidances, European Union GCP Directive 2005/28/EC, the ICH Guideline for GCP, Section 4.8, and the terms of the Declaration of Helsinki (2013). Copies of the signed document should be given to the patient and filed in the Investigator's study file, as well as the patient's medical record if in conformance with the institution's Standard Operating Procedures.

10.2 Institutional Review Board/Independent Ethics Committee

The study will not be initiated without approval of the appropriate IRB/IEC and compliance with all administrative requirements of the governing body of the institution. This protocol, consent procedures, and any amendments must be approved by the IRB/IEC in compliance with current regulations of the FDA and the European Union as applicable and in accordance with ICH/GCPs. A letter of approval will be sent to the Sponsor prior to initiation of the study and when any subsequent modifications are made. The IRB/IEC will be kept informed by the Investigator, Sponsor's monitoring CRO or the Sponsor, as required by national regulations, as to the progress of the study as well as to any serious and unexpected AEs.

10.3 Patient Privacy

In order to maintain patient confidentiality, all eCRFs, study reports and communications relating to the study will identify patients by initials and assigned patient numbers; patients should not be identified by name. In accordance with local, national or federal regulations, the Investigator will allow the Sponsor or designee personnel access to all pertinent medical records in order to verify the data gathered on the eCRFs and to audit the data collection process. Regulatory agencies such as the US FDA may also request access to all study records, including source documentation for inspection. Clinical information will not be released without the written permission of the patient as outlined in the patient consent form.

11.0 DATA HANDLING AND RECORD KEEPING

11.1 Data to be Entered Directly in the Case Report Form

The eCRF will be the source record.

11.2 Recording of Data

Data collected during the study will be entered in the patient's eCRF by the investigational site staff. The staff will keep records of the patient's visit in the files considered as source documents for the site, e.g., hospital chart, research chart. The Investigator will be responsible for the recording of all data on the eCRF and for submitting the data to the Sponsor or their designee in a timely manner. Should any value be significantly different from normal, the Investigator will comment in the appropriate sections provided in the eCRF.

The Investigator will provide access to his/her original records to permit a representative from the Sponsor to verify the proper transcription of data.

11.3 Study Records

U.S. Federal laws require that an Investigator maintain all study records for the indication under investigation for two years following the date a Product Licensing Application is approved or, if no application is to be filed or if the application is not approved for such indication, until two years after the investigation is discontinued and the FDA is notified.

APPENDIX I - Cockcroft-Gault Equation

Males:

$$\text{Creatinine CL (mL/min)} = \frac{\text{Weight (kg)} \times (140 - \text{Age})}{72 \times \text{serum creatinine (mg/dL)}}$$

Females:

$$\text{Creatinine CL (mL/min)} = \frac{\text{Weight (kg)} \times (140 - \text{Age})}{72 \times \text{serum creatinine (mg/dL)}} \times 0.85$$

APPENDIX II - ECOG Performance Status

Grade

0	Fully active, able to carry on all pre-disease performance without restriction.
1	Restricted in physically strenuous activity but ambulatory and able to carry out work of a light or sedentary nature, e.g., light housework, office work.
2	Ambulatory and capable of all self-care but unable to carry out any work activities. Up and about more than 50% of waking hours.
3	Capable of only limited self-care, confined to bed or chair more than 50% of waking hours.
4	Completely disabled. Cannot carry on any self-care. Totally confined to bed or chair.
5	Dead.

APPENDIX III - Acceptable Contraceptive Methods

• Male or female condom with or without spermicide• Cervical cap, diaphragm or sponge with spermicide

Highly Effective Contraceptive Methods That Are User Dependent ^a
 
Failure rate of <1% per year when used consistently and correctly.
 
• Combined (estrogen- and progesterone-containing) hormonal contraception ^b
◦ Oral◦ Intravaginal◦ Transdermal◦ Injectable• Progestogen-only hormonal contraception ^b
◦ Oral◦ Injectable

Highly Effective Methods That Have Low User Dependency
 
Failure rate of <1% per year when used consistently and correctly.
 
• Progesterone-only contraceptive implant ^{b, c}• Intrauterine hormone-releasing system (IUS) ^b• Intrauterine device (IUD)• Bilateral tubal occlusion

• Vasectomized partner
 
A vasectomized partner is a highly effective contraception method provided that the partner is the sole male sexual partner of the female of childbearing potential and the absence of sperm has been confirmed. If not, an additional highly effective method of contraception should be used.


• Sexual abstinence
 
Sexual abstinence is considered a highly effective method only if defined as refraining from heterosexual intercourse during the entire period of risk associated with the study treatment. The reliability of sexual abstinence needs to be evaluated in relation to the duration of the study and the preferred and usual lifestyle of the participant.)
 
Notes:
 
Use should be consistent with local regulations regarding the use of contraceptive methods for participants of clinical studies.
 
a) Typical use failure rates are lower than perfect-use failure rates (i.e., when used consistently and correctly).
 
b) If hormonal contraception efficacy is potentially decreased due to interaction with study treatment, condoms must be used in addition to the hormonal contraception during the treatment period and for at least 120 days, (corresponding to time needed to eliminate study treatment plus 30 days for study treatments with genotoxic potential) after the last dose of the study treatment.
 
c) If locally required, in accordance with Clinical Trial Facilitation Group (CTFG) guidelines, acceptable hormonal contraceptives are limited to those which inhibit ovulation.

APPENDIX IV - New York Heart Association (NYHA) Classification

NYHA Grading		MET*
Class I	No limitations. Ordinary physical activity does not cause undue fatigue, dyspnea or palpitations (asymptomatic LV dysfunction)	>7
Class II	Slight limitation of physical activity. Ordinary physical activity results in fatigue, palpitation, dyspnea or angina pectoris (mild Congestive Heart Failure (CHF)).	5
Class III	Marked limitation of physical activity. Less than ordinary physical activity leads to symptoms (moderate CHF)	2 – 3
Class IV	Unable to carry on any physical activity without discomfort. Symptoms of CHF present at rest (severe CHF).	1.6

*MET (metabolic equivalent) is defined as the resting VO_2 for a 40-year-old 70kg man.
1 MET = 3.5 mL O_2 /min/kg body weight.

APPENDIX V - Lugano Criteria for RT Patients⁵⁵

Response and Site	PET-CT-Based Response	CT-Based Response
Complete	Complete metabolic response	Complete radiologic response (all of the following)
Lymph nodes and extra-lymphatic sites	Score 1, 2, or 3* with or without a residual mass 5 PS [†] It is recognized that in Waldeyer's ring or extranodal sites with high physiologic uptake or with activation within spleen or marrow (e.g., with chemotherapy or myeloid colony-stimulating factors), uptake may be greater than normal mediastinum and/or liver. In this circumstance, complete metabolic response may be inferred if uptake at sites of initial involvement is no greater than surrounding normal tissue even if the tissue has high physiologic uptake	Target nodes/nodal masses must regress to ≤ 1.5 cm in LD _i No extralymphatic sites of disease
Nonmeasured lesion	Not applicable	Absent
Organ enlargement	Not applicable	Rgress to normal
New lesions	None	None
Bone marrow	No evidence of FDG-avid disease in marrow	Normal by morphology; if indeterminate, IHC negative
Partial	Partial metabolic response	Partial remission (all of the following)
Lymph nodes and extra-lymphatic sites	Score of 4 or 5 [†] with reduced uptake compared with baseline and residual mass(es) of any size At interim, these findings indicate responding disease At end of treatment, these findings indicate residual disease	≥ 50% decrease in SPD of up to 6 target measurable nodes and extranodal sites When a lesion is too small to measure on CT, assign 5 mm × 5 mm as the default value When no longer visible, 0 × 0 mm For a node > 5 mm × 5 mm, but smaller than normal, use actual measurement for calculation
Nonmeasured lesions	Not applicable	Absent/normal, regressed, but no increase
Organ enlargement	Not applicable	Spleen must have regressed by >50% in length beyond normal
New lesions	None	None

Bone marrow	Residual uptake higher than uptake in normal marrow but reduced compared w/ baseline (diffuse uptake compatible w. reactive changes from chemotherapy allowed). If there are persistent focal changes in the marrow in the context of a nodal response, consideration should be given to further evaluation w/ MRI or biopsy or an interval scan	Not applicable
No response or stable disease	No metabolic response	Stable disease
Target nodes/nodal masses, extranodal lesions	Score 4 or 5 with no significant change in FDG uptake from baseline at interim or end of treatment	<50% decrease from baseline in SPD of up to 6 dominant, measurable nodes and extranodal sites; no criteria for progressive disease are met
Non measure lesions	Not applicable	No increase consistent with progression
Organ enlargement	Not applicable	No increase consistent with progression
New lesions	None	None
Bone marrow	No change from baseline	Not applicable
Progressive disease	Progressive metabolic disease	Progressive disease requires at least 1 of the following
Individual target nodes/nodal masses	Score 4 or 5 with an increase in intensity of uptake from baseline and/or	PPD progression:
Extranodal lesions	New FDG-avid foci consistent with lymphoma at interim or end-of-treatment assessment	An individual node/lesion must be abnormal with: LDi >1.5 cm and Increase by ≥50% from PPD nadir and an increase in LDi or SDi from nadir 0.5 cm for lesions ≤2 cm 1.0 cm for lesions >2 cm In the setting of splenomegaly, the splenic length must increase by >50% of the extent of its prior increase beyond baseline (e.g., a 15-cm spleen must increase to >16 cm). If no prior splenomegaly, must increase by at least 2 cm from baseline New or recurrent splenomegaly

Non measured lesions	None	New or clear progression of preexisting nonmeasured lesions
New lesions	New FDG-avid foci consistent with lymphoma rather than another etiology (e.g., infection, inflammation). If uncertain regarding etiology of new lesions, biopsy or interval scan may be considered	Regrowth of previously resolved lesions A new node >1.5 cm in any axis A new extranodal site >1.0 cm in any axis; if <1.0 cm in any axis, its presence must be unequivocal and must be attributable to lymphoma Assessable disease of any size unequivocally attributable to lymphoma
Bone marrow	New or recurrent FDG-avid foci	New or recurrent involvement

Revised Response Criteria (Table Key)

Abbreviations: 5PS, 5-point scale, CT computed tomography; FDG, fluorodeoxyglucose; IHC, immunohistochemistry; LDi, longest transverse diameter of a lesion; MRI, magnetic resonance imaging; PET, positron emission tomography; PPD cross product of the LDi and perpendicular diameter; SDi, shortest axis perpendicular to the LDi; SPD, sum of the product of the perpendicular diameters for multiple lesions.

*A score of 3 in many patients indicates a good prognosis with standard treatment, especially if at the time of an interim scan. However, in trials involving PET where de-escalation is investigated, it may be preferable to consider a score of 3 as inadequate response (to avoid undertreatment). Measured dominant lesions: Up to 6 of the largest dominant nodes, nodal masses, and extranodal lesions selected to be clearly measurable in two diameters. Nodes should preferably be from disparate regions of the body and should include, where applicable, mediastinal and retroperitoneal areas. Non-nodal lesions include those preferably be from disparate regions of the body and should include, where applicable, mediastinal and retroperitoneal areas. Non-nodal lesions include those in solid organs (e.g., liver, spleen, kidneys, lungs), GI involvement, cutaneous lesions, or those noted on palpation. Nonmeasured lesions: Any disease not selected as measured, dominant disease and truly assessable disease should be considered not measured. These sites include any nodes, nodal masses, and extranodal sites not selected as dominant or measurable or that do not meet the requirements for measurability but are still considered abnormal, as well as truly assessable disease, which is any site of suspected disease that would be difficult to follow quantitatively with measurement, including pleural effusions, ascites, bone lesions, leptomeningeal disease, abdominal masses, and other lesions that cannot be confirmed and followed by imaging. In Waldeyer's ring or in extranodal sites (e.g., GI tract, liver, bone marrow), FDG uptake may be greater than in the mediastinum with complete metabolic response, but should be no higher than surrounding normal physiologic uptake (e.g., with marrow activation as a result of chemotherapy or myeloid growth factors).

[†]PET 5 PS: 1, no uptake above background; 2 uptake \leq mediastinum; 3, uptake $>$ mediastinum but \leq liver; 4, uptake moderately $>$ liver; 5, uptake markedly higher than liver and/or new lesions; X, new areas of uptake unlikely to be related to lymphoma.

APPENDIX VI - Dose Modifications of Venetoclax with Use of CYP3A or P-gp Inhibitors

Concomitant use of venetoclax with *strong* CYP3A inhibitors at initiation and during ramp-up phase is contraindicated. Concomitant use of venetoclax with *strong* CYP3A inhibitors increases venetoclax exposure (i.e., C_{max} and AUC) and may increase the risk for TLS at initiation and during ramp-up phase. For patients who have completed the ramp-up phase and are on a steady daily dose of venetoclax, reduce the venetoclax dose by at least 75% when *strong* CYP3A inhibitors must be used concomitantly.

Avoid concomitant use of venetoclax with *moderate* CYP3A inhibitors or P-gp inhibitors. Consider alternative treatments. If a *moderate* CYP3A inhibitor or a P-gp inhibitor must be used, reduce the venetoclax dose by at least 50%. Monitor these patients more closely for signs of toxicities.

Resume the venetoclax dose that was used prior to initiating the CYP3A inhibitor or P-gp inhibitor 2 to 3 days after discontinuation of the inhibitor.

The recommendations for managing drug-drug interactions are summarized in the table below.

Co-administered drug	Initiation and Ramp-Up Phase	Steady Daily Dose (After Ramp-Up Phase)
Posaconazole	Day 1 – 10 mg Day 2 – 20 mg Day 3 – 50 mg Day 4 – 70 mg	Reduce venetoclax dose to 70 mg.
Other strong CYP3A inhibitor	Day 1 – 10 mg Day 2 – 20 mg Day 3 – 50 mg Day 4 – 100 mg	Reduce venetoclax dose to 100 mg.
Moderate CYP3A inhibitor	Reduce the venetoclax dose by at least 50%	
P-gp inhibitor		

Warfarin

Concomitant use of venetoclax increases warfarin C_{max} and AUC_{inf} , which may increase the risk of bleeding. Closely monitor international normalized ratio (INR) in patients using warfarin concomitantly with venetoclax.

P-gp Substrates

Concomitant use of venetoclax increases C_{max} and AUC_{inf} of P-gp substrates, which may increase toxicities of these substrates. Avoid concomitant use of venetoclax with a P-gp substrate. If a concomitant use is unavoidable, separate dosing of the P-gp substrate at least 6 hours before venetoclax.

Please refer to the venetoclax USPI⁵⁶ for additional details on drug-drug interactions.

Below (Table 20) are examples of CYP3A inhibitors and inducers (strong and moderate); however,

this is not an exhaustive list.

Table 20. CYP3A Inhibitors and Inducers

CYP3A Inhibitors	
Strong CYP3A Inhibitors	Moderate CYP3A Inhibitors
boceprevir, cobicistat, danoprevir and ritonavir, elvitegravir and ritonavir, indinavir and ritonavir, itraconazole, ketoconazole, lopinavir and ritonavir, paritaprevir and ritonavir and (ombitasvir and/or dasabuvir), posaconazole, ritonavir, saquinavir and ritonavir, telaprevir, tipranavir and ritonavir, telithromycin, troleandomycin, voriconazole	aprepitant, ciprofloxacin, conivaptan, crizotinib, cyclosporine, diltiazem, dronedarone, erythromycin, fluconazole, fluvoxamine, imatinib, tofisopam, verapamil
CYP3A Inducers	
Strong CYP3A Inducers	Moderate CYP3A Inducers
apalutamide, carbamazepine, enzalutamide, mitotane, phenytoin, rifampin, St. John's wort	bosentan, efavirenz, etravirine, phenobarbital, primidone

Note: In addition to the medications listed above, patients taking venetoclax should not consume grapefruit, grapefruit products, Seville oranges, (including marmalade containing Seville oranges), or star fruit.

VENETOCLAX DRUG DIARY

Instructions:

You will use this diary to record each dose of venetoclax that you take. You should also use this diary to record any side effects that you experience and medications that you take other than the venetoclax. Please be sure to bring this diary with you to your next clinic visit.

Venetoclax:

- Venetoclax is taken once a day every day, approximately 24 hours apart.
- Venetoclax should be taken with food. Venetoclax can be taken before or after start of APR-246 infusion (± 2 hours).
- If you forget to take a dose of venetoclax and it is within 8 hours of when it should have been taken, you should take the dose. If it has been more than 8 hours, you should skip that dose and take the next dose at the next regular time.
- If you vomit after taking a dose of venetoclax, you should not make up the dose or take additional pills, you should take the next dose at the next regular time.
- Always bring your pill bottles (including those that are empty) and your diary with you to each clinic visit.

Your study doctor will make sure you reach the required dose of venetoclax slowly, over the period of 5 weeks called ramp-up, as shown in the table below.

Week Number	Venetoclax Daily Dose
Week 1	20 mg
Week 2	50 mg
Week 3	100 mg
Week 4	200 mg
Week 5 and beyond	400 mg

If you have any questions, please ask a study team member or your doctor.

Patient Number: _____

STUDY STAFF USE ONLY

Patient Initials: _____

Staff member reviewing diary at end of study
cycle:

Cycle Number: _____

Start Date: _____

Venetoclax tablets to take at each dose: 20 mg = _____

50 mg = _____

100 mg = _____

Other information/Comments:

VENETOCLAX DRUG DIARY (continued)

Patient Number/Initials: _____

Cycle: _____

Cycle Day	Date Taken	Time Taken	Number of venetoclax tablets taken	Dose taken	Comments (Side effects, complaints, other medications)
1					
2					
3					
4					
5					
6					
7					
8					
9					
10					
11					
12					
13					
14					
15					
16					
17					
18					
19					
20					
21					
22					
23					
24					
25					
26					
27					
28					

* NOTE: Add additional days in case needed due to scheduling delay or dose modifications.

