4.0 TRIAL DESIGN

4.1 Overview of Trial Design

Treatment will be administered on an outpatient basis but may be administered in the inpatient setting for patients who are hospitalized and meet criteria for study enrollment. No investigational or commercial agents or therapies other than those described below may be administered with the intent to treat the patient's disease under study.

Monotherapy Cycle

There is a 7-day monotherapy cycle where patients receive APR-246 IV on Day 1 and APR-246 PO on Day 2. The primary purpose of the monotherapy cycle is to obtain peripheral blood for monotherapy PK and PD analyses following IV and PO administration of APR-246.

Patients will start treatment with APR-246 IV as a single agent administered on Day 1 of a single 7-day monotherapy cycle at the assigned cohort dose level, prior to Cycle 1 Day 1 of combination therapy. On Day 2 of the 7-day monotherapy lead-in period, patients will receive a single dose of APR-246 administered PO at the dose of 500 mg. After review of oral PK data from at least 6 patients, a decision can be made whether to increase the PO dose of APR-246 and/or administer APR-246 with a standard high-fat meal to investigate, respectively, dose linearity in PK and/or the effect of food on oral absorption of APR-246. Dose escalation of the oral dose or switching to administration with food will be determined by PK to ensure that the APR-246 exposure levels after oral dosing do not exceed the exposure levels after IV administration in terms of C_{max} and AUC.

Combination Treatment

After the APR-246 monotherapy lead-in, study treatment will consist of APR-246 administered as an IV infusion at the same assigned dose that was used during the monotherapy lead-in period once weekly, on Days 1, 8 and 15 of each cycle, concurrently with venetoclax for the 5-week ramp-up at the dose of 20 mg during Week 1, 50 mg during Week 2, 100 mg during Week 3, 200 mg during Week 4, and 400 mg during Week 5. Beginning Cycle 2 Day 1, venetoclax will be administered at 400 mg (or tolerable dose following 5-week ramp up) PO daily. IV rituximab will be initiated at 375 mg/m² on Cycle 2, Day 2 and then administered at 500 mg/m² on Day 2 of Cycles 3-7. After 6 cycles of treatment with APR-246 in combination with venetoclax + rituximab, APR-246 + venetoclax will continue to be

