5.3.3 Venetoclax

5.3.3.1 Dosage Modifications Based on Toxicities

Interrupt dosing or reduce dose for toxicities. See tables below for recommended dose modifications for toxicities related to venetoclax. For patients who have had a dosing interruption greater than 1 week during the first 5 weeks of ramp-up phase or greater than 2 weeks after completing the ramp-up phase, reassess for risk of TLS to determine if re-initiation with a reduced dose is necessary. Please consult full prescribing information in USPI⁴⁷, as clinically warranted, and Section [5.2](#) for management of overlapping toxicities.

Table 13. Recommended Venetoclax Dose Modifications for Toxicities

Event	Occurrence	Action
Tumor Lysis Syndrome		
Blood chemistry changes or symptoms suggestive of TLS	Any	Withhold the next day's dose. If resolved within 24 to 48 hours of last dose, resume at the same dose.
		For any blood chemistry changes requiring more than 48 hours to resolve, resume at a reduced dose.
		For any events of clinical TLS resume at a reduced dose following resolution.
Non-Hematologic Toxicities		
Grade 3 or 4 nonhematologic toxicities	1 st occurrence	Interrupt venetoclax. Once the toxicity has resolved to grade 1 or baseline level, venetoclax therapy may be resumed at the same dose. No dose modification is required.
	2 nd and subsequent occurrences	Interrupt venetoclax. Follow dose reduction guidelines in the table below when resuming treatment with venetoclax after resolution. A larger dose reduction may occur at the discretion of the physician.
Hematologic Toxicities		
Grade 3 neutropenia with infection or fever, or grade 4 hematologic toxicities (except lymphopenia)	1 st occurrence	Interrupt venetoclax. To reduce the infection risks associated with neutropenia, granulocyte-colony stimulating factor (G-CSF) may be administered with venetoclax if clinically indicated. Once the toxicity has resolved to grade 1 or baseline level, venetoclax therapy may be resumed at the same dose.
	2 nd and subsequent occurrences	Interrupt venetoclax. Consider using G-CSF as clinically indicated. Follow dose reduction guidelines in the table below when resuming treatment with venetoclax after resolution. A larger dose reduction may occur at the discretion of the physician.

Consider discontinuing venetoclax for patients who require dose reductions to less than 100 mg for more than 2 weeks.

Table 14. Dose Reduction for Toxicity During Venetoclax Treatment

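### For patients past ramp-up on less than 400 mg venetoclax, Appendix VI's percentage cut for strong CYP3A inhibitors conflicts with the fixed doses in its own table and in Table 15

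*Combined protocol and SAP*

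**What the plan says.** Appendix VI states one rule in prose and another in the table beneath it.

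- **Prose.** For a patient who has finished ramp-up and must take a strong CYP3A inhibitor: "on a steady daily dose of venetoclax, reduce the venetoclax dose by at least 75"%. For moderate CYP3A inhibitors and P-gp inhibitors: "reduce the venetoclax dose by at least 50"%.
- **Appendix VI table, steady-dose column.** It is introduced as a summary of the prose: "The recommendations for managing drug-drug interactions are summarized in the table below". The posaconazole row says "Reduce venetoclax dose to 70 mg" and the row for other strong inhibitors says "Reduce venetoclax dose to 100 mg". The moderate and P-gp rows keep the 50% rule.
- **Table 15 (Section 5.3.3.2).** It repeats the 70 mg and 100 mg entries. Neither table ties them to a starting dose of 400 mg.
- **Table 20.** Posaconazole is on the list of strong inhibitors ("ombitasvir and/or dasabuvir), posaconazole, ritonavir"), so the 75% rule covers it too.

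Steady doses below 400 mg are expected. Section 4.1 says that from Cycle 2 "venetoclax will be administered at 400 mg (or tolerable dose following 5-week ramp up) PO daily". For second and later grade 3 or 4 non-hematologic events, and for second and later qualifying hematologic events, Table 13 says "Follow dose reduction guidelines in the table below when resuming treatment with venetoclax after resolution". Table 14 then steps down from 400 to 300, 200, 100 mg and lower.

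**The concern.** The prose rule scales with the current dose and the table rule does not. They can agree only over part of the dose range, and the protocol does not say which prevails elsewhere. A site that reads only the table would give a reduced-dose patient more venetoclax than the prose permits, alongside a drug that Appendix VI itself says raises venetoclax Cmax and AUC.

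Two features make this more than tidiness. First, TLS aside, Table 13 lowers the dose only after a second qualifying event, so some of these patients have already had repeated severe toxicity. Second, the two conditions can coincide. Recurrent neutropenia with fever or infection lowers the venetoclax dose. It also prompts a review of prophylaxis (Table 5), with antifungals to be considered (Table 8). Section 5.3.2.3 foresees triazole antifungals being started on treatment, and Table 20 lists posaconazole, voriconazole and itraconazole as strong inhibitors.

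Venetoclax PK is not sampled (Section 8.9), so an excess would not show in the PK data. If it occurred in Cycle 2 or 3, resulting toxicity could count as a DLT under Section 5.1.4, though that case is narrow.

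**Working it through.** **Inputs.** Prose cut with a strong inhibitor: at least 75% (Appendix VI). Fixed doses: 100 mg, or 70 mg with posaconazole (Appendix VI table, Table 15). Cut with a moderate inhibitor: at least 50% (same places). Steady doses D: 400, 300, 200 and 100 mg (Section 4.1, Table 14). Doses below 100 mg are left out because Section 5.3.3.1 already says to consider stopping venetoclax if they last more than 2 weeks.

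**Formulas.** Prose ceiling = 0.25 × D. Cut implied by a fixed dose F = 1 − F/D. Ratio to the prose ceiling = F/(0.25 × D). Moderate-inhibitor ceiling = 0.5 × D. Ratio to the moderate ceiling = F/(0.5 × D).

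**Check at the planned dose.** At D = 400 mg the prose ceiling is 0.25 × 400 = 100 mg, exactly the table entry. For posaconazole, 1 − 70/400 = 82.5%, which also satisfies the prose. There is no conflict at 400 mg.

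**All steady doses.**

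| D (mg) | Prose ceiling (mg) | 100 mg: cut | 100 mg ÷ prose ceiling | 70 mg: cut | 70 mg ÷ prose ceiling |
|---|---|---|---|---|---|
| 400 | 100 | 75% | 1.0 | 82.5% | 0.70 |
| 300 | 75 | 66.7% | 1.33 | 76.7% | 0.93 |
| 200 | 50 | 50% | 2.0 | 65% | 1.4 |
| 100 | 25 | 0% | 4.0 | 30% | 2.8 |

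**Where each entry stops complying.** The 100 mg entry needs D of at least 100/0.25 = 400 mg. The 70 mg entry needs D of at least 70/0.25 = 280 mg. On the Table 14 steps, the first fails from 300 mg down and the second from 200 mg down.

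**Order of the table rows.**

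| D (mg) | Moderate ceiling (mg) | 100 mg ÷ moderate ceiling | 70 mg ÷ moderate ceiling |
|---|---|---|---|
| 400 | 200 | 0.50 | 0.35 |
| 300 | 150 | 0.67 | 0.47 |
| 200 | 100 | 1.0 | 0.70 |
| 100 | 50 | 2.0 | 1.4 |

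At 200 mg the row for other strong inhibitors equals the moderate ceiling. At 100 mg both strong-inhibitor rows allow more than the moderate row, the reverse of the order at 400 mg.

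**The case against.** The best defence is that the table is the rule worked out at the standard dose, and that anything else goes to the label: Section 4.3.2 says steady-dose changes for posaconazole and CYP inhibitors follow the venetoclax USPI. On this view the 4.0 ratio is artificial, because an instruction to reduce to 100 mg cannot be carried out at 100 mg and would prompt a query. The larger gaps also arise mostly after repeated toxicity, when Tables 5 and 6 bring in the Medical Monitor at the third occurrence. Strong inhibitors are restricted: exclusion 19 bars certain ones at entry, Table 15 asks for alternatives, and the prose applies only when they must be used. Appendix VII, on prohibited medications, is not in the text available here and may restrict them further. Finally, a lower-of-two rule is new wording and takes every patient on 300 mg or less below 100 mg.

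Part of this stands. The event is likely to be rare, the matter is minor, and the documents do not show which rule was intended. The rest does not remove the conflict. No text confines the fixed doses to 400 mg, and going from 300 or 200 mg to 100 mg is an executable step that breaks the prose. The USPI is outside the documents, and citing it leaves both instructions in force. The Medical Monitor consultation concerns resuming treatment after toxicity, not starting an inhibitor. The doses below 100 mg already follow from the existing 75% rule.

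**Conclusion.** The concern holds. At 400 mg the instructions agree. Below that, the 100 mg entry exceeds the prose ceiling at every step, by factors of 1.33, 2.0 and 4.0 at 300, 200 and 100 mg. The posaconazole entry exceeds it by factors of 1.4 and 2.8 at 200 and 100 mg. These ratios take the prose as the yardstick. If the sponsor intends the fixed doses to govern, the prose is what must change, and the reversed order of the rows at 100 mg would still need correcting. This is a minor dosing-safety inconsistency that should be fixed. The sample size, which rests on no power calculation, is unaffected.

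**What to change.** In the steady-dose column of both tables, for strong inhibitors, state: reduce to 100 mg (70 mg with posaconazole) or to 25% of the current dose, whichever is lower, rounded down to a dose the available tablets can give; if that is not feasible, interrupt venetoclax or consult the Medical Monitor. Align the Appendix VI prose, and have the sponsor confirm the rule clinically.

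Assuming 10 mg steps (10 mg is the lowest dose in Table 14), the results from 400, 300, 200 and 100 mg are:

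- other strong inhibitors: 100, 70, 50 and 20 mg;
- posaconazole: 70, 70, 50 and 20 mg.

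Each is below the matching moderate-inhibitor ceiling of 200, 150, 100 and 50 mg, so the order of the rows is restored. Also state whether the Section 5.3.3.1 prompt to consider stopping venetoclax after more than 2 weeks below 100 mg applies to these interaction cuts.

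The cost is wording in three places, and the ramp-up column of the same tables can be revised in the same edit. The downside is somewhat lower venetoclax exposure in a few reduced-dose patients while the inhibitor is given. No extra patients or data are needed.
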